### 3.12 POPULATIONS FOR ANALYSES

The primary analysis will be based on an intention-to-treat (ITT) population, including all participants randomized. Secondary analyses will be based on a modified intention-to-treat (MITT) population consisting of all participants who received at least one dose of the study medications.

## 4.0 STATISTICAL ANALYSES

### 4.1 DESCRIPTIVE STATISTICS

Baseline characteristics representing demographic, clinical history, symptom, and biomarker variables will be summarized by treatment arms. The distribution of each variable will be examined. All variables will be summarized using appropriate central tendency (mean/median) and spread measures (standard deviation, 25th and 75th percentiles, or range) for continuous variables and frequency and percent for categorical variables.

### 4.2 ANALYSIS OF THE PRIMARY EFFICACY ENDPOINT

As a primary approach, the primary endpoint CE30 will be compared between two arms using a two-sample Z-statistic for proportion (standardized difference between proportion having CE in the anticoagulant arm and matching placebo arm, positive difference favoring anticoagulant arm). More explicitly, denoting  $p$ ,  $p_A$  and  $p_P$  the estimated proportion of CE30 in the whole sample, anticoagulant and placebo group respectively, the null hypothesis of no difference in the proportions will be tested using the test statistic

$$Z = (p_P - p_A) / SE(p_P - p_A),$$

where  $SE(p_P - p_A)$  will be estimated by pulling over the two groups, that is,

$$SE(p_P - p_A) = \sqrt{[p(1-p) \left( \frac{1}{n_P} + \frac{1}{n_A} \right)]},$$

where  $n_P$  and  $n_A$  are the sample sizes for the placebo and anticoagulant groups, respectively.

The CE30 rates will also be modeled using a log-binomial regression model with treatment arm as the independent variable and adjusting for trial stratification variables (i.e., antiplatelet use; WHO ordinal scale score). Secondary analyses of this endpoint will include adjustment for D-dimer levels, intensive care unit stay, patient characteristics, and demographic factors, including race and ethnicity. The matching placebo arm will serve as the “reference group” in this model, and analysis will involve testing whether the coefficient for each active treatment group relative to the reference group is equal to 0, or equivalently, whether the adjusted relative risk for the anti-coagulant arm is equal to 1. The adjusted relative risk and the related confidence interval will be provided.

In addition, unadjusted event rates for each treatment group, and relative risk and the absolute risk differences with confidence intervals, will be calculated and presented. Kaplan-Meier cumulative incidence curves will also be presented to allow visualization of the patterns of time to first events. As a sensitivity analysis, a modified intention-to-treat analysis, excluding all randomized participants who fail to initiate treatment, will be conducted.

Patients dropping out of the study prior to day 30 will contribute data up to the time of drop-out.

- Sensitivity Analyses

The primary analysis will be repeated in the MITT analysis population where subjects who did not start the medication will be excluded. For all supplemental and sensitivity analyses, p-values will be

reported and 95% confidence levels will be used for confidence interval estimates. The tabular and graphical summaries described in the previous section will be replicated for the MITT analysis.

The primary analysis will also be repeated using the other subgroups defined in Section 4.6. Each subgroup will be considered separately, and the tabular and graphical summaries described in the previous section will be replicated for each subgroup. In addition, a forest plot will be generated to display the overall treatment difference estimate and CI from each of the within-stratum analyses. These analyses will be performed in the ITT and MITT populations.

The primary analysis uses information from participants who dropped out up to the time of the drop-out. A tipping points sensitivity analysis that systematically and comprehensively varies assumptions about the missing outcomes on the two treatment arms will be applied. These analyses will be two-dimensional and will allow assumptions about the missing outcomes on the two arms to vary independently. These scenarios will include those where dropouts on drug tend to have worse outcomes than dropouts on control. The goal is to explore the plausibility of missing data assumptions under which the conclusions change, i.e., under which there is no longer evidence of efficacy.

Further supplementary analyses of the primary endpoint will include the use of Fisher's exact test, Cochran-Mantel-Haenszel test adjusting for stratification factors. Furthermore, a random intercept log-binomial regression of the primary outcome with baseline characteristics including stratification factors and a random intercept for the recruitment site will be performed to assess factors associated with the primary outcome.

To understand the time course of the primary event CE, we will use Kaplan-Meier curves to estimate the cumulative proportion of events over time. Differences between such proportions over time by treatment groups will be assessed using log-rank test adjusting for stratification factors and will further be investigated using Cox proportional hazard models. In addition to the stratification factors, the Cox model will assess other baseline patient characteristics.

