8.1 Enrollment/Randomization

Enrollment

1. Hospitalized patients confirmed COVID-19 positive are screened daily for inclusion/exclusion criteria. Any patient who meets all inclusion criteria and no exclusion criteria will be approached for enrollment.

2. Patients remain in the intention-to-treat group.

Randomization

Randomization assignments are performed for patients at baseline visit. Randomization will be done with equal probability across the arms for which the participant is eligible. For Stage 1, randomization stratification will be done by anti-platelet use (yes/no) and WHO severity score (<5 / >=5).

The randomization scheme will be determined by the study *Stage* and its associated group of intervention arms. Randomization should obviate the need for additional adjustment factors, but if pre-specified demographic or clinical characteristics are unbalanced with respect to treatment group, an adjustment will be considered during the analyses phase; these characteristics include but are not limited to age, sex, race, ethnicity, BMI, and, potentially, country.

9. Source Documents and Access to Source Data/Documents

ACTIV-4 will have uniform policies describing what source documents are, how to make corrections, and who can access them.

10. Quality Assurance and Quality Control

ACTIV-4 will have common policies for quality assurance at the data entry level and site monitoring.

11. Ethics/Protection of Human Subjects

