### 3.5 POWER AND SAMPLE SIZE

The primary analysis for this randomized trial will be an intention-to-treat comparison of a composite endpoint (CE) of venous thromboembolic events, including new, symptomatic proximal or distal deep vein thrombosis affecting the upper and/or lower extremities, pulmonary embolism, or thrombosis of other veins (e.g., cerebral sinus veins, splanchnic veins); arterial thromboembolic events, including new ischemic stroke, myocardial infarction, mesenteric or peripheral arterial thromboembolism; and all-cause mortality for up to 30 days after randomization across the intervention arms. This binary primary endpoint was used to power the study.

The MARINER trial reported a 2% event rate for a combined outcome of VTE, MI, CVA, or CV deaths in the placebo group (Spyropoulos, 2018). These rates are expected to be higher in COVID-19 patients who are discharged from the hospital. Recent information from patients discharged alive from the University of Pittsburgh Medical Center suggests that the 30-day mortality rate in this population could be as high as 4%. To be conservative, 4% was used as the expected CE rate of events for the no anticoagulant arm. An effect size of 35% percent risk reduction (risk ratio = 0.65) in the anticoagulant group compared to the no anticoagulant group was used to calculate the expected sample size for the study.

The analysis will use a group-sequential two-sample two-sided Z-test for proportions with pooled standard deviation to test the primary hypothesis at overall significance two-sided level alpha = 0.05. Four equally spaced interim analyses and one final analysis will use O'Brien-Fleming alpha spending boundaries for efficacy and the Hwang-Shih-DeCani boundaries for the futility reviews (O'Brien and Fleming, 1979; Hwang, Shih, and De Cani, 1990). In order to ensure an 80% power to detect a CE rate reduction of 35% through anticoagulation use, the study needs to enroll at least 2,530 participants per arm. Since the primary outcome is observed within 30 days of follow-up, the loss to follow-up and withdrawal of consent rates should be low, and it is estimated that CE will be missing on a maximum of 5% of the participants. Therefore, the sample size required for this study will be approximately 2,660 per

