### 3.6 RANDOMIZATION SCHEME

Randomization will be performed for study participants as close to the time of hospital discharge as possible. Hospitalized patients may be screened and approached about the study up to 48 hours before hospital discharge, but final enrollment and randomization should occur as close to the time of discharge as possible. Participants will be randomized in a 1:1 ratio using an online randomization system to either Arm A (apixaban 2.5 mg twice daily), or Arm B (matching placebo). Randomization will be stratified by (1) concomitant use of a single antiplatelet agent (yes/no), and (2) a maximal score of 5 or greater vs. a score of less than 5 by the World Health Organization (WHO) Ordinal Index.

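### The deciding test of CE30, and the Z read against the stopping boundaries, ignore the strata used in randomisation: a small, conditional loss of efficiency and coherence, not a validity error

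*SAP*

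**What the plan says.** - **Randomisation.** SAP 3.6: "Randomization will be stratified by (1) concomitant use of a single antiplatelet agent (yes/no), and (2) a maximal score of 5 or greater" versus below 5 on the WHO scale. Protocol 2.2 agrees. This gives four strata.
- **Deciding test.** SAP 4.2: "the primary endpoint CE30 will be compared between two arms using a two-sample Z-statistic for proportion". Its standard error is sqrt[p(1-p)(1/nP + 1/nA)], with p the event proportion in the whole sample. Protocol 7.3 has the same test.
- **Stopping.** The boundary tables in SAP 3.7.2 and Protocol 7.6.4 refer to that same Z. Futility is assessed at all interim looks and efficacy from the third.
- **Sizing.** SAP 3.5 uses the pooled Z without strata, at "overall significance two-sided level alpha = 0.05".
- **Stratum-adjusted analyses.** SAP 4.2 plans a log-binomial model with both factors and, among the supplementary analyses, a "Cochran-Mantel-Haenszel test adjusting for stratification factors". The log-rank test is also adjusted for the factors.
- **Secondary endpoints.** In SAP 4.3 the proportional-odds models for QOL&M30 and QOL&M90 include both factors. CE45, CE90, CEVTE30 and CEATE30 follow the primary procedure and so inherit the unstratified Z.

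**The concern.** Stratified randomisation balances the arms within strata. If event risk differs between strata, part of the outcome variance lies between them and can no longer contribute to chance differences between the arms. The whole-sample p(1-p) still counts that part, so the pooled standard error is too large and |Z| too small.

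The plan is also uneven. Both factors enter the log-binomial model, the log-rank test and the models for the first two key secondary endpoints, but not the CE30 test that gates all six secondary endpoints. The documents give no reason for this. Near a boundary, the test that decides could miss it while the stratified test crosses it.

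At stake is a little power, and agreement between the deciding analysis and the design.

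**Working it through.** **Inputs from SAP 3.5 and 3.6.** Placebo rate 4% ("4% was used as the expected CE rate of events for the no anticoagulant arm"); risk ratio 0.65, hence 2.6% on apixaban; two-sided alpha 0.05; 80% power; 1:1 allocation; 2,530 evaluable per arm. **Not in the documents:** stratum shares and stratum risk ratios. These are assumed below. The factors are taken as independent, the treatment risk ratio as common to all strata, and balance within strata as exact.

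**1. The plan's own figure.** With pooled p = (0.04 + 0.026)/2 = 0.033:

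n = [1.96 sqrt(2 x 0.033 x 0.967) + 0.8416 sqrt(0.04 x 0.96 + 0.026 x 0.974)]^2 / 0.014^2 = 2,555 per arm.

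The plan has 2,530, which is 1.0% lower. Fixed-sample power at 2,530 is 79.6%. Inflating for missing outcomes, 2,530/0.95 = 2,663, against a stated figure of about 2,660. The sizing therefore reproduces with the unstratified test.

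**2. Size of the overstatement.** Let w_s be the stratum share and p_s the stratum risk averaged over the arms.

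- Pooled variance: P(1-P) = 0.033 x 0.967 = 0.031911.
- Within-stratum variance: W = sum of w_s p_s(1-p_s).
- The difference is the between-stratum part, sum of w_s(p_s - P)^2. It is zero if the factors are not prognostic.

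**3. Worked example.** Take 25% antiplatelet users, 20% with WHO score 5 or more, and risk ratios 1.5 and 2.5.

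- Shares are 0.60, 0.20, 0.15 and 0.05; risk multipliers are 1, 1.5, 2.5 and 3.75, with weighted mean 1.4625.
- Baseline risk is 0.033/1.4625 = 0.02256, so the p_s are 0.02256, 0.03385, 0.05641 and 0.08462.
- The between-stratum part is 0.000281, W = 0.031630, and the ratio 0.031911/0.031630 = 1.009.
- Null SE: sqrt(2 x 0.031911/2530) = 0.005023 pooled; sqrt(2 x 0.031630/2530) = 0.005000 stratified. The within-stratum SE under the alternative is 0.004996.
- Power = Phi[(0.014 - 1.96 x null SE)/0.004996], which is 79.7% pooled and 80.0% stratified.

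**4. Range.** Shares and risk ratios are antiplatelet/WHO. The last column is 2,530 x (1 - W/0.031911).

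| Shares | Risk ratios | W | Null variance overstated by | Power, pooled to stratified | Gain (points) | Equivalent patients per arm |
|---|---|---|---|---|---|---|
| 20%/20% | 1/1.5 | 0.031875 | 0.1% | 79.63% to 79.66% | 0.03 | about 3 |
| 25%/20% | 1.5/2.5 | 0.031630 | 0.9% | 79.7% to 80.0% | 0.2 | about 22 |
| 30%/25% | 2/4 | 0.031101 | 2.6% | 79.9% to 80.6% | 0.7 | about 64 |

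**5. Simulation check** (400,000 binomial trials, fixed sample, balanced strata). Two-sided type I error, pooled Z against CMH, is 0.0490 against 0.0500 in the second row and 0.0466 against 0.0500 in the third. Three further profiles gave 0.0492 against 0.0497 (risk ratios 1.5/2), 0.0493 against 0.0510 (2/3) and 0.0450 against 0.0497 (3/5). The pooled test stays below 0.05 throughout. Only the steep 3/5 profile takes the simulated power gain above one point, from 80.5% to 81.7%.

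**The case against.** The strongest reply is that nothing here is invalid. The unadjusted Z is pre-specified, matches the test used for sizing, and does not inflate type I error. Stratum-adjusted results will be reported anyway, so only the ranking of planned analyses is in dispute. Enrolment began in February 2021, so the change would alter the deciding statistic of a running group-sequential trial whose operating characteristics SAP 3.5 says were already simulated. All of that stands, and it limits the point to a minor improvement. It does not show any advantage in letting the unstratified test decide.

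A reader might infer more, in four ways:

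- **That the standard error is certainly too large.** This needs prognostic factors, and no section says they were chosen for prognosis. Protocol 7.6 describes its subgroup factors, these two being the main ones, as possible modifiers of the treatment effect. That is a different property.
- **That the boundaries are wrong.** Their values do not depend on stratification. Only the Z compared with them does.
- **That observed imbalance chooses the primary model.** Protocol 8.1 says "if pre-specified demographic or clinical characteristics are unbalanced with respect to treatment group, an adjustment will be considered during the analyses phase", but it names age, sex, race, ethnicity, BMI and possibly country, not the stratification factors. SAP 4.2 fixes the primary test and makes covariate adjustment secondary.
- **That the bleeding analysis has the same defect.** SAP 4.4 plans proportions, relative risks and risk differences with intervals and names no test, so no defect follows there.

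Stratifying would not remove every possible disagreement either, since the unstratified Z would still be reported. It would make the deciding result the one that matches the randomisation.

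**Conclusion.** The mismatch between stratified randomisation and an unstratified deciding test is clear from the text. Its direction is conditional: if the factors are prognostic, the test is slightly conservative. Its size is small, at 0.1% to 2.6% of the null variance and about 0.03 to 0.7 power points over the assumed profiles. It is zero without prognostic strata and exceeds one point only with gradients steeper than those in the table. These are fixed-sample figures at a critical value of 1.96; the gain at each look has not been traced. They rest on assumed shares and risk ratios. This is a worthwhile minor improvement in efficiency and coherence, and it is no reason to doubt the validity of the primary test.

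**What to change.** The blinded statisticians, who alone may modify the SAP after the first unblinded review (SAP 1.0), should amend SAP 4.2 and 3.7.2, with matching text in Protocol 7.3 and 7.6.4:

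- Make the CMH Z, stratified by antiplatelet use and WHO score, the primary statistic at all interim looks and the final analysis. Report a Mantel-Haenszel risk difference with its confidence interval.
- Add a rule for sparse strata. At the first look there would be about 0.2 x 2,530 = 506 evaluable per arm. With 20%/20% shares and risk ratios 1.5/2 (assumed), the smallest stratum holds 4% of these, about 20 per arm. At a pooled risk of 7.5% that is about 3 events over both arms. The rule should say which strata are merged and when, using counts pooled over the arms.
- Keep the unstratified Z as a supportive analysis.
- Use the same stratified test for CE45, CE90, CEVTE30 and CEATE30 (SAP 4.3, Protocol 7.4 and A5.5).

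The boundary values, sample size and data collection do not change. The cost is amended wording and a brief repeat of the operating-characteristic simulations with the stratified statistic.

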### 3.7.2 INTERIM ANALYSES FOR FUTILITY AND EFFICACY REVIEW

The trial design planned for 4 interim analyses and a final analysis at equally-spaced information points. At each interim analysis cumulative primary outcome data, and potentially the secondary analyses, will be presented to the DSMB. Based on the data, a decision to stop or continue the trial will be taken following the O'Brien-Fleming Rule. If the Z-statistic crosses the lower boundary, the trial will be stopped for futility while if the Z-statistic crosses the upper boundary, the trial will be stopped declaring anticoagulant to be effective in preventing CE. In either case, Stage 1 of the trial will end and secondary analyses, including subgroup analyses will be critical for driving adaptive changes made based on accrued data. Eligibility criteria, efficacy, and safety endpoints will be analyzed at predefined intervals to guide the design of subsequent stages to allow efficient use of data and resources to inform the adaptations in trial design.

Assessments of futility will be conducted at all interim looks, whereas efficacy will only be assessed starting at the third interim analysis (after 60% of the information accumulated; **Table 1**). For the efficacy and futility, O'Brien-Fleming analog alpha-spending function and Hwang-Shih-DeCani beta-spending function will be utilized to create the non-binding boundaries. **Table 1** and **Figure 2** provide specific efficacy and futility boundaries at each interim analysis.

**Table 1:** Stopping Boundaries for Efficacy and Futility based on Z-statistic above.

Look	Information fraction	Efficacy Boundary	Futility Boundary
1	20%	NA	0.1383
2	40%	NA	-0.5933
3	60%	-2.6686	-1.1439
4	80%	-2.2887	-1.5918
Final	100%	-2.0307	-2.0307

**Figure 2:** Stopping Boundaries for Efficacy and Futility based on the Z-statistic described above.

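### SAP 4.2 gives no sequentially adjusted estimate or interval for the primary endpoint, so the benefit reported after an early efficacy stop would on average be too large, chiefly at the 60% look

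*SAP*

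**What the plan says.** SAP 3.5 plans four interim analyses and a final one, tested at "overall significance two-sided level alpha = 0.05". SAP 3.7.2 adds that "efficacy will only be assessed starting at the third interim analysis", which is at 60% information. The efficacy boundaries in its Table 1 are 2.6686, 2.2887 and 2.0307 in absolute value at 60%, 80% and 100%. The boundaries are described as non-binding.

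On estimation, SAP 4.2 (and Protocol 7.3 in the same terms) says that unadjusted event rates, "relative risk and the absolute risk differences with confidence intervals, will be calculated and presented". It gives no interval level and no sequential method. The level appears only in the paragraph on supplemental and sensitivity analyses: "95% confidence levels will be used for confidence interval estimates". The estimand table in SAP 3.2 makes the difference in proportions the primary summary measure.

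SAP section 1.0 speaks of interim-analysis methods only as controlling type I error. Neither document mentions a repeated confidence interval, a stage-wise interval, or a bias-adjusted or median-unbiased estimate.

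**The concern.** A trial stops for efficacy at look 3 only if the observed effect is large enough to pass 2.6686. Selecting on a high observed value means that the estimate reported at the stop is, on average, above the truth. The plan corrects the test for this but not the estimate or its interval.

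This is not a rare route. At the planned effect, 59 of about 79 percentage points of power come from early efficacy stops. The size of benefit would then be set against bleeding: Protocol Appendix 3 (A3.3) provides for a risk-benefit review, and SAP 4.4 reports absolute bleeding differences. An overstated absolute benefit tilts that comparison.

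**Working it through.** **Inputs.** Placebo rate: "4% was used as the expected CE rate of events for the no anticoagulant arm". Risk ratio 0.65, so 2.6% on apixaban and a true risk difference (RD) of 1.40 points. Sample size: "the study needs to enroll at least 2,530 participants per arm". Looks at 20, 40, 60, 80 and 100%, so looks 3, 4 and 5 have 1,518, 2,024 and 2,530 per arm. Boundaries are from SAP Table 1, turned so that benefit is positive, as in the SAP 4.2 formula for Z.

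**The plan's own figure.** The SAP's aim is stated as: "In order to ensure an 80% power to detect a CE rate reduction of 35% through anticoagulation use".
- Fixed-sample n = [1.96·√(2·0.033·0.967) + 0.8416·√(0.04·0.96 + 0.026·0.974)]² / 0.014² = (0.4952 + 0.2125)² / 0.000196 ≈ 2,555 per arm, within 3% of 2,530.
- Group-sequential power at 2,530 with the efficacy boundaries only is 78.7% (multivariate normal) or 79.0% (simulation).
- The boundaries spend cumulative one-sided alpha of 0.0038, 0.0122 and 0.0250, as O'Brien-Fleming-type spending should.
- 2,530/0.95 ≈ 2,664, which fits about 2,660.

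**Why look 3 selects.** With placebo at 4%, Z = RD / √[p(1−p)·2/1,518] reaches 2.6686 only when RD is at least 1.69 points, 1.21 times the planned effect. At look 4 the minimum is 1.30 points, 0.93 times the planned effect.

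**Simulation at the planned effect** (1 to 2 million binomial trials, pooled Z, Wald 95% intervals, futility stops not applied; the relative risk reduction, RRR, figures are rounded):

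| Efficacy stop | Share of trials | Mean RD | RD excess | RRR excess | 95% CI coverage |
|---|---|---|---|---|---|
| Look 3 | 30% | 2.14 | +53% | about +39% | 92% |
| Look 4 | 29% | 1.56 | +12% | about +10% | about 100% |
| Either | 59% | 1.86 | +33% | about +25% | 96% |

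Example: 2.14/1.40 = 1.53. If futility stops are obeyed, early efficacy stops fall to 56% and the pooled excess is 34%.

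**Other true effects** (placebo 4%). At RR 0.75 the mean RD is about 1.8 times the truth over early efficacy stops, 2.11 at look 3 and 1.56 at look 4. At RR 0.55 the ratios are about 1.13, 1.23 and 0.88, so a look-4 stop then understates the benefit.

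**Coverage.** Over all trials at the planned effect it is 95.1%, or 93.4% if futility is obeyed. At RR 0.55 with futility obeyed it is 91.0%. After a look-3 efficacy stop it is 92% at RR 0.65, 80% at RR 0.75 and 73% at RR 0.775. In the last case such a stop occurs in about 9% of trials. Intervals that use the boundary constant cover 99% (RR 0.65) and 96% (RR 0.775) after a look-3 stop.

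**Agreement with the boundary.** 2.6686 and 2.2887 both exceed 1.96, so an ordinary 95% interval always excludes no effect at an early efficacy stop. A mismatch needs a final Z between 1.96 and 2.0307. That happens in 1.8% of trials at the planned effect, or 0.8% if futility is obeyed.

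**What the candidate corrections do to a typical look-3 stop.** With RD 2.14, placebo 4% and apixaban 1.86%, p = 0.0293 and SE = √(0.0293·0.9707·2/1,518) = 0.612 points.
- Ordinary interval: 2.14 ± 1.96·0.612 = 0.94 to 3.34.
- Repeated interval: 2.14 ± 2.6686·0.612 = 0.51 to 3.77. The point estimate is unchanged.
- Stage-wise median-unbiased estimate: 2.14 (0.94 to 3.34), the same as unadjusted, because this is the first efficacy look.
- Bias adjustment averaged over all stopping outcomes (the usual Whitehead form): the simulated mean over all trials, futility ignored, is 1.072·1.40 = 1.50 when the truth is 1.40, and 1.048·1.80 = 1.89 when it is 1.80. So it removes only about 0.1 point. With futility obeyed the ratios are 0.91 and 0.99, and it removes nothing.
- The same adjustment made conditional on an efficacy stop at look 3: the mean of such stops is 2.14 when the truth is 1.40, so an observed 2.14 maps to 1.40. It is unstable: at RR 0.75 the look-3 mean is 2.11·1.00 = 2.11, so an observed 2.11 maps to 1.00.

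**The case against.** A reader might infer that any early stop inflates the benefit by a third to a half. It does not. That span joins the pooled figure (+33%) to look 3 alone (+53%), on the RD scale and at the planned effect only. Look 4, nearly half of early stops, gives +12%.

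A reader might also infer that the intervals are generally too narrow, or can contradict the boundary at an early stop. Coverage over all trials and over all early efficacy stops is near nominal at the planned effect, and contradiction is possible only at the final look. Even there the Z boundary decides, so no success claim is at risk.

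Other points against:
- The SAP does not prescribe fixed-sample or 95% intervals for the primary RD and RR. Both are inferred from its silence. This stands, though no other method is offered.
- Participants randomized but short of day 30 at the stop would dilute the bias if added. The documents give no accrual rate. If those added amount to 5%, 10% or 20% of planned n (an assumption), the look-3 excess falls to 49%, 45% or 40%; for example (1,518·2.14 + 253·1.40)/1,771 = 2.03, and 2.03/1.40 = 1.45. The bias is smaller but remains.
- The exploratory Bayesian analysis in SAP 4.5 has a skeptical prior. By a normal approximation without the site effect, it would move a look-3 RR of 0.515 to about 0.67. That is useful shrinkage, but it is exploratory and does not replace the main estimate.
- A repeated interval does not repair the point estimate. This stands, and the fix has to allow for it.

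**Conclusion.** The gap is real and limited to reporting. The plan adjusts the primary test for five looks and leaves estimation unspecified. Read naturally, it would report an unadjusted RD that is on average 53% too large after a look-3 efficacy stop and 12% after look 4. The excess is greater if apixaban works less well than planned, and less if it works better or if participants still in follow-up are added. Interval under-coverage belongs mainly to look-3 stops, most of all when the effect is smaller than planned.

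These sizes assume the planned rates, 2,530 evaluable per arm, looks exactly as scheduled, and an analysis of the data at the stopping look. Type I error and the stopping decision are unaffected. This is a cheap improvement.

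**What to change.** Add to SAP 4.2, for the primary RD and RR, beside the unadjusted estimates:
- **A repeated confidence interval** using the efficacy boundary constant of the stopping look, recomputed from the spending function at the actual information fraction (2.6686, 2.2887 or 2.0307 if looks fall as planned). It agrees with the boundary decision by construction.
- **A bias-adjusted (Whitehead-type) point estimate**, stating whether it averages over all stopping outcomes or is conditional on the stopping look. Only the conditional form answers the look-3 bias. Label it as a sensitivity figure, because it is unstable near the boundary.
- **A sentence of caution** that the unadjusted estimate after an early efficacy stop is expected to overstate the benefit.
- **The dataset used**: the stopping look, or that plus participants who complete day 30 afterwards.

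The cost is a few sentences and standard group-sequential methods, with no new data and no design change. Intervals widen by 2.6686/1.96 = 1.36, 2.2887/1.96 = 1.17 and 2.0307/1.96 = 1.04 at looks 3, 4 and final, and are conservative overall (about 97% coverage).
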